**C.1.c. Functional Magnetic Resonance Imaging (fMRI)**

**Exerience.** [name] (Co-I) developed a Cannabis Cue Reactivity (CCR) fMRI task consisting of cannabis and neutral images that is useful for probing the neurobehavioral effects of gabapentin: 1) cue reactivity appears to be GABA/GLU mediated, 2) cue reactivity/craving are important clinical targets, and 3) reward sensitivity (congruent with the RDoC construct, Approach Motivation), arguably best characterized by CCR in CUD+BD, is a core neurobehavioral deficit in both CUD and BD.

**Figure 3. Robust activation was elicited from cannabis, vs. neutral, stimuli in heavy cannabis users in reward regions including the medial prefrontal cortex, anterior cingulate and striatum.**

Preliminary data, from 41 heavy (M=2x/day) cannabis users (46% women, M age=18.7 ±0.51) demonstrated significant activation to cannabis vs. neutral cues (cluster-corrected z > 2.3, p < 0.05) in regions involved in reward processing, including bilateral medial prefrontal, striatum, dACC, subcallosal, precuneus, and posterior cingulate cortex (Figure 3). As noted in C.2.e (Procedures), the proposed response inhibition ("go no-go") fMRI task, included to better target dACC activation) has been featured in a number of PI-authored publications.

**C.2. Research Design and Methods.** The proposed 2-week, double-blind crossover study will evaluate: a) the effects of gabapentin on basal dACC and rBG GABA and GLU concentrations and b) the effects of changes in GABA and GLU levels on brain activity to cannabis and response inhibition (impulsivity) cues. The relationship between changes in GABA and GLU levels, brain activation to cannabis/response inhibition cues, and clinical symptoms (e.g., cannabis use, impulsivity, mood and anxiety) will be explored. Participants will complete two, 1-week experimental conditions (gabapentin, placebo) in a randomized order. Each condition will consist of a visit for assessment and dispensing of medication (Day 1), titration to maximum dose (1200mg/day) (Days 1-5), MRI (Day 5), and medication washout (Days 5-7). Spacing of appointments cited throughout the protocol refers to ideal conditions which may be minimally deviated from if needed (e.g., +/- 1 day between medication and MRI visits, 1 week between conditions). See Figure 4 below for a full study design schematic.

[figure not shown]

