the study if the provider feels it is appropriate. Concerning the RHJVAMC, we will seek separate approval through the VAMC to post and distribute VA-approved study fliers.

Table 1. Schedule of events by study visit					
Study Visit	Visit 1 Evaluation	Visit 2 Med Disp	Visit 3 MRI	Visit 4 Med Disp	Visit 5 MRI
Clinician and PA					
Informed Consent* / HIPAA* / BrAC contract*	X				
SCID-5 (Mood/Substance)*	X				
TLFB* (90 day at V1)	X	X	X	X	X
YMRS* / MADRS* / C-SSRS*	X	X	X	X	X
BDRS / BR		X	X		X
Observe Dose (note time)		X	X	X	X
H&P* / Metal Screen*	X				
AEs / Vitals		X	X	X	X
Self-Report					
Demographics / Family history	X				
BDI* / PSQI* / BAI*	X				
BIS-11 / SPSRQ / AUDIT / ASRS / WHODAS / DSM-5 PID5/PQ	X				
BDI PW / PSQI PW / BAI PW (PW=Past Week)		X	X		X
FTND / ASRM / MCQ / CWS	X	X	X		X
Actiwatch Data Download			X	X	X
Urge to use MJ [1-10] (PRE/POST MRI)					X
Computer Tasks					
STOP-IT	X		X		X
Delay Disc	X				
GoGoNoGo Practice			X		
CNL Labs					
CMP* / CBC* / DNA*	X				
%dCDT		X			
Gabapentin level			X		X
EtG		X	X		X
Riboflavin		X	X		X
Cannabinoids/Creatinine Levels		X	X	X	X
In-House Labs					
Collect urine specimen* / UDS*	X	X	X	X	X
Breathalyzer*	X	X	X	X	X
Pregnancy Test*	X		X		X
Saliva drug screen		X	X		X

Note: "\*" Indicates assessments that must be done at Visit 1. Non-starred assessments at Visit 1 can be completed at Visit 2 if needed.

**C.2.e. Procedures.** See Table 1.

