inclusion/exclusion determination and not completed at Visit 1 at Visit 2. At Visit 2, participants will be asked to wear an actigraphy watch (Actiwatch Spectrum Plus, Philips Respironics) on their non-dominant wrist for the remainder of the study. They will be instructed on its use (e.g., not to take it off when showering) and asked to keep a brief actigraph log (e.g., sleep and wake times) delivered daily via text/e-mail using REDCap. On day 1 of each condition, mood symptoms (YMRS, MADRS, C-SSRS) and alcohol/drug consumption (TLFB, UDS) will be assessed. Medications will be packaged and dispensed by the MUSC Investigational Drug Service (IDS). IDS will oversee blinding procedures for the study and maintain treatment assignment records. Medication will be over-encapsulated with riboflavin (25mg/capsule), for urinary detection by fluorescence spectroscopy at each MRI, with each capsule containing either 300mg of gabapentin or matching placebo dispensed in blister packs. At each Dispensing visit, participants will take their first dose in front of study staff to ensure compliance. They will receive detailed instructions regarding the dosing schedule for days 1-5 of the condition (See Figure 4). Gabapentin has an elimination half-life of 6-7 hours. Participants should reach steady state concentrations of the maximal dose (1200mg) well before the MRI visit. Twice daily dosing will be used to maximize compliance. The proposed titration schedule is consistent with our experience with gabapentin for AUD, gabapentin studies in CUD, and our clinical experience with dual diagnosis patients. Unused medications will be returned for pill counts. Gabapentin blood levels will be obtained for all participants, in house, using a validated immunoassay. Medication adherence will be evaluated as a covariate. Due to flexibility in scheduling (+/- 1 day for the MRI visit), extra medication will be provided for each participant and labeled as such to ensure participants have the correct number of doses.

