**MRI (Visits 3, 5).** MRI visits will take place on day 5 of each condition. Participants will be asked to abstain from drugs/alcohol  $\geq 12$  hours prior to MRI. They will take their final dose of medication in front of study staff, 1 h prior to MRI, to ensure compliance. Participants who smoke will be allowed to have their last cigarette immediately prior to their final medication dose. Mood symptoms (YMRS, MADRS, C-SSRS, BDI, BAI, ASRM, PSQI), alcohol/drug/tobacco consumption (TLFB, UDS, FTND, EtG, Saliva), cannabis withdrawal (CWS), and cravings (MCQ) will be assessed. Participants will provide a urine and blood sample to test for gabapentin levels, riboflavin, liver function, and alcohol/drug consumption. Following structural and H-MRS scanning, participants will complete the CCR and go no-go fMRI tasks in counterbalanced order (see below) with the Natural Rewards Task at the end. fMRI tasks will be conducted while acquiring BOLD weighted transverse scans using a gradient-echo, echo-planar imaging (EPI) sequence: TR/TE=2200/35 ms; flip angle=90°; field of view=220x220 mm; voxel size=3.00x3.00 mm; 37 contiguous 3-mm-thick slices. Total scan time is approximately 75 m in a Siemens 3.0T Prisma (32-channel head coil). Participants will discontinue study medication following each MRI and will remain off study medication on days 6-7 of the condition. Given that the last gabapentin dose will be taken in the morning of day 5, this will provide approximately 11 half-lives of elimination prior to the start of the next condition. Crossover studies employing up to 3x the proposed dose of gabapentin have demonstrated an absence of carryover effects on clinical outcomes given the same or fewer days of washout as proposed herein. Potential carryover effects will be carefully examined using the proposed analytic design. Outside of the scanner, participants will complete the STOP-IT task. Within approximately 72 hours of day 7 of the final study condition, participants will be contacted by clinically-trained study staff to discuss adverse events, alcohol and drug consumption, and mood stability since discontinuing study medication.

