**b. Source of Materials.** Data collected from participants will include breathalyzer readings, urine drug screens, urine biomarkers (e.g., riboflavin, ethyl glucuronide), blood chemistries, structural, functional, and neurochemical MRI brain images, and interviews and self-reports regarding substance use, psychiatric diagnoses, concomitant medications, and adverse events. To ensure confidentiality, all participant data will be number-coded, and only the investigators will have access to the master list of codes. A federal Certificate of Confidentiality, protecting participants against disclosure of sensitive information (e.g., drug use), will be obtained for the study.

**c. Compensation.** To maximize participant retention, contingency management will be applied to participant compensation such that participants will be compensated significantly more for each subsequent MRI visit they

attend (i.e., scan 1 = \$100, scan 2 = \$150), and participants will be given an additional \$50 bonus for completing both MRI visits without rescheduling and for returning their actigraphy watch. Participants will be compensated \$10/hour (rounded to the nearest half-hour) during the diagnostic visit if screened out during this time. Participants will be compensated \$50 for completing the full initial psychiatric and medical evaluation appointment. Finally, participants will be compensated \$30 for each additional non-MRI appointment (i.e., 2 total). Following the initial appointment, participants will be compensated weekly, at the end of each MRI session; \$50 of each week's compensation will be contingent on them returning their actigraphy watch to the appointment. Total compensation will thus be \$410 per participant. In our experience, this level of compensation is fair for the time commitment required without unduly coercing participants to enroll in the study despite potential concerns.

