**Pregnancy.** Gabapentin is rated as a Category C medication in terms of pregnancy. Because there are no adequate controlled studies of gabapentin in pregnant women, it is unknown whether the drug can cause fetal harm or affect reproductive capacity in humans. Therefore, women of childbearing potential must agree to pregnancy testing and use of adequate contraception in order to be eligible to participate in the study. Females will be given a urinary pregnancy test at the screening visit and weekly thereafter. Any female participant who becomes pregnant during the study will be discontinued from the study medication and removed from study participation. For all included females of childbearing potential, current forms of birth control and date of last menstruation will be assessed at each study visit.

Confidentiality. Records with identifying information (e.g., consent documents) will be stored in a locked file. All other non-MRI participant data will be collected via direct data capture (REDCap); MRI data will be automatically transferred to Linux-based servers managed by CBI. Both MRI and non-MRI data will be stored in restricted access directories on password-protected, encrypted servers managed by CBI and the Department of Psychiatry and Behavioral Sciences at MUSC. Participants will be given an ID number for all MRI and non-MRI data files. The master list of codes will be accessible only to the investigators, and will be stored in a locked office. As noted above, a federal Certificate of Confidentiality, protecting participants against disclosure of sensitive information (e.g., drug use), will be obtained prior to study initiation.

Emergencies. All study participants will be instructed how to access the 24-hour on-call system available at the Medical University of South Carolina. In the event that a participant experiences an adverse event after hours, s/he will be instructed to access the 24-hour on-call service. If it is determined that the participant needs immediate help, the participant may be advised to immediately go to the emergency room. In that event, proper medical treatment will be administered, per ER procedures. [name] and [name] will be available by pager/cell as necessary. The Investigational Drug Service (IDS) will be available 24 hours/day, 7 days/week for emergency identification of treatment group assignment and unblinding as necessary.

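### No pregnancy test is scheduled at the dispensing visits, so the Visit 1 test is the only scheduled one before first exposure to study drug

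*Combined protocol and SAP*

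**What the plan says.** The rule on frequency is in Protection of Human Subjects, section 2.c, Pregnancy: "Females will be given a urinary pregnancy test at the screening visit and weekly thereafter". The same paragraph removes any participant who becomes pregnant from drug and from the study. It also has birth control and date of last menstruation assessed at each visit. Exclusion criterion 11 in section 1.a bars women who are pregnant.

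The schedule is in Table 1. The row "Pregnancy Test" is marked at Visits 1, 3 and 5, with blank cells at Visits 2 and 4, both headed as medication dispensing. The row is starred, and the table note explains the star: "Indicates assessments that must be done at Visit 1". The row "Collect urine specimen* / UDS" is marked at all five visits.

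Dosing is in section C.2.e. Under Medication Dispensing (Visits 2, 4): "At each Dispensing visit, participants will take their first dose in front of study staff to ensure compliance". Under MRI (Visits 3, 5), which take place on Day 5: "They will take their final dose of medication in front of study staff, 1 h prior to MRI, to ensure compliance".

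**The concern.** The protocol excludes pregnant women, and stops drug if pregnancy occurs, because it regards the fetal risk of gabapentin as unknown. These protections work best if pregnancy status is checked when exposure starts. As scheduled, it is checked once at screening and next on the day dosing ends. A pregnancy that becomes detectable after Visit 1 but by Visit 2 would pass the dispensing visit without a test.

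What is at stake is a few days of possible gabapentin exposure in a participant whom the protocol means to exclude. No endpoint, sample size or analysis is involved.

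**Working it through.** The plan states no figure to reproduce. The check sets the schedule beside the dosing text and counts days.

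**Inputs**
- Visit 2 is Day 1 and Visit 3 is Day 5 of the first condition (C.2 and C.2.e). With two one-week conditions, Visit 4 is nominally Day 8 and Visit 5 is Day 12.
- The MRI visit may move by 1 day either way (C.2; C.2.e, Medication Dispensing).
- Let g be the number of days from Visit 1 to Visit 2. The readable text does not give it. Section 2.c, Medical Risks, requires the study physician to review a blood panel before study medication starts, so Visit 2 has to wait at least for that. No maximum is stated. The values of g below are assumptions.

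**First condition**
- Age of the Visit 1 test at first dose = g days.
- Visit 1 to Visit 3 = g + (5 − 1) = g + 4 days, or g + 3 to g + 5 with the MRI window.
- Nominally this exceeds a week when g + 4 > 7, that is, when g > 3.

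| Assumed g | Test age at first dose | Visit 1 to Visit 3, nominal | With MRI window |
|---|---|---|---|
| 3 days | 3 days | 7 days | 6 to 8 days |
| 7 days | 7 days | 11 days | 10 to 12 days |
| 14 days | 14 days | 18 days | 17 to 19 days |

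Dosing days completed before the day of the Visit 3 test do not depend on g. They are 3 if the MRI is on Day 4, 4 if on Day 5, and 5 if on Day 6. The final dose of the condition is taken at that same visit. The text does not say whether the test or the dose comes first, so stopping drug can prevent at most that one dose in the first condition.

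**Second condition, nominal calendar**
- Age of the Visit 3 test at Visit 4 = 8 − 5 = 3 days (8 − 6 = 2 to 8 − 4 = 4 with the window).
- Visit 3 to Visit 5 = 12 − 5 = 7 days (11 − 6 = 5 to 13 − 4 = 9 with both windows).

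Both intervals grow if the conditions are spaced further apart. The wording of that allowance in C.2 is ambiguous, so no figure is given for it.

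**With a Visit 2 test**
- Test age at the first dose of the first condition = 0 days.
- Visit 2 to Visit 3 = 5 − 1 = 4 days (3 to 5 with the window).

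**The case against.** The strongest reply is that the text already limits the age of the test. The weekly rule runs from the screening visit. Read literally, it leaves no test more than about 7 days old at first dose, and a 14-day gap without a further test would be a protocol deviation. That is a fair reading, and it is why one cannot say that the plan permits a test of any age. But no visit in Table 1 carries the extra test, so staff working from the schedule would not do it.

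A reader might go the other way and infer a flat contradiction between text and table. The documents do not support that either. Section 1.c, Compensation, uses the same word for the MRI visits ("participants will be compensated weekly, at the end of each MRI session"), and C.2 defines the conditions by the week ("Participants will complete two, 1-week experimental conditions (gabapentin, placebo) in a randomized order"). If weekly means once per condition, Visits 3 and 5 satisfy it. On that reading, too, no test is tied to the first dose.

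A reader might also treat Visit 4 as an equal gap. It is not: the Visit 3 test is nominally 3 days old at that point.

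Or a reader might infer that a positive Visit 3 result comes too late to matter. It comes late for the first condition, but removal from the study prevents the whole second condition. A participant given placebo first would then receive no gabapentin at all.

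Finally, contraception is an eligibility condition, and birth control and last menstruation are asked about at the dispensing visits. These lower the risk, but they are questions rather than a test, and the readable text attaches no repeat test to the answers.

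**Conclusion.** The point holds in a limited form. No scheduled pregnancy test coincides with a first dose, and the Visit 1 test is the only scheduled one before first exposure. A pregnancy that becomes detectable between Visits 1 and 2 would reach a scheduled test only at Visit 3, after 3 to 5 completed dosing days. The second condition would still be prevented.

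How old the Visit 1 test can be at first dose cannot be settled from what is readable. It depends on g and on how the weekly rule is read, and Figure 4 may show the spacing. If g is 3 days or less, the nominal Visit 1 to Visit 3 interval is within a week and the point shrinks to the lack of a same-day test.

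The risk is small: dosing lasts about 5 days per condition, one of the two conditions is placebo, and contraception is required. This is a desirable safety improvement with no bearing on power or analysis.

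**What to change.** Mark the pregnancy test at Visit 2 in Table 1, done on the urine already collected there and read before the first dose. Keep the tests at Visits 1, 3 and 5. Reword the frequency sentence in section 2.c, Pregnancy, to match, for example: at screening, before the first dose at Visit 2, and at each MRI visit.

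A Visit 4 test is optional on the nominal calendar, where the Visit 3 test is 2 to 4 days old. It is worth doing if the conditions are spaced further apart.

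The cost is one table cell, one sentence and one strip per woman of childbearing potential: at most 1 × 23 = 23 strips if all 23 enrolled were such women. With Visit 4 included, the maximum is 2 × 23 = 46. No visit or specimen collection is added, and power and analysis are unchanged.

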### **3. Potential Benefits of the Proposed Research to the Subjects and Others**

Benefits to the subjects include medical and psychiatric assessments provided at no cost. Subjects may benefit by reduction of cannabis consumption as an effect of active treatment or through nonspecific effects of study participation (increased awareness of cannabis consumption, frequent interactions with study personnel, etc.), although this is not guaranteed for any given subject. Other individuals with comorbid CUD and BD are likely to benefit by the knowledge gained from the study as it may help guide future treatments.

### **4. Importance of the Knowledge to Be Gained**

There is a six-fold increase in the prevalence of CUD in individuals with BD relative to the general population; this common comorbidity is associated with substantially elevated negative outcomes, including treatment resistance. Treatment research for co-occurring CUD and BD is extremely limited, with no randomized trials for CUD+BD conducted to date. The proposed study will evaluate the ability of a medication (i.e., gabapentin) that has been shown to increase cortical GABA levels in past research to manipulate a neurochemical dysfunction characteristic of individuals with CUD+BD (i.e., dysregulated brain GABA/glutamate homeostasis). Positive results may support investigation of gabapentin for the treatment of CUD+BD in large-scale, randomized clinical trials. Furthermore, the proposed study may provide successful demonstration of a neurobehavioral, multimodal neuroimaging platform for evaluating the potential promise of GABAergic drugs for CUD and/or BD, as well as other conditions marked by GABA/glutamate dysfunction. The proposed investigation's minimal risks are reasonable in relation to the importance of the knowledge to be gained from the investigation.

### **5. Clinicaltrials.gov Requirements**

In accordance with Public Law 110-85, this project will be registered at the ClinicalTrials.gov Protocol Registration System Information Website prior to study initiation.

## **Data and Safety Monitoring Plan**

This section is based on the recommendations in NIDA's "Guidelines for Developing a Data and Safety Monitoring Plan".

### 1) Summary of the Protocol.

This application proposes to investigate the effects of gabapentin on brain GABA and glutamate concentrations, a neurobehavioral measure of cannabis cue-reactivity, and mood and cannabis use in individuals with co-occurring cannabis use disorder and bipolar disorder. The primary outcomes of interest are brain GABA and glutamate levels and a neurobehavioral measures of cannabis cue-reactivity. Inclusion/exclusion criteria are outlined in Protection of Human Subjects. Power calculations and sample sizes are detailed in the Sample Size Determination section of the Research Strategy.

### 2) Trial Management.

The study will be managed from the Addiction Sciences Division within the Department of Psychiatry and Behavioral Sciences at the Medical University of South Carolina (MUSC). The target population is described above in the inclusion/exclusion criteria.

### 3) Data Management and Analysis.

Non-MRI data will be collected via direct data capture (REDCap) on tablet devices and stored on MUSC centralized secured, backed-up servers. MRI data will be automatically transferred to Linux-based servers managed by the Center for Biomedical Imaging (CBI). The data analysis plan is outlined in the Data Analysis section of the Research Strategy.

### 4) Quality Assurance.

Quarterly data audits will be conducted. Confidentiality protections are outlined above.

### 5) Regulatory Issues.

Potential conflicts of interest will be reported using the upcoming NIH rules for disclosure. Adverse Events (AEs)/Serious Adverse Events (SAEs) occurring during the course of the project will be collected, documented, and reported in accordance with protocol and Institutional Review Board (IRB) reporting requirements. All research staff involved with adverse event reporting will receive general and protocol specific AE/SAE training including identification, assessment and evaluation, and documentation and reporting. A research assistant will identify any potential adverse events during the course of the study from participant self-report and administration of the visit assessments and procedures. The research assistant will provide information to a study physician, who will be responsible for AE/SAE assessment and evaluation including a determination of seriousness and study relatedness. Any significant actions taken by the local IRB and protocol changes will be relayed to NIDA.

